Heart rate	Since both fast and slow heart rate may be harmful and there is no universal definition of abnormal heart rate under anesthesia, we will model using a variety of methods. 
 1. Maximum change (BPM) from preoperative heart rate (positive and negative) 2. Relative change (%) from preoperative heart rate (positive and negative) 3. Maximum pulse variation (maximum heart rate minus minimum heart rate) 4. Longest single episode (minutes) a) below 60, and b) above 100BPM 5. Cumulative duration (minutes) a) below 60, and b) above 100BPM
Use of hemodynamic medications (i.e. special medications for blood pressure)	
 1. Vasopressor/inotrope use (yes vs. no): phenylephrine, norepinephrine, epinephrine, vasopressin, dobutamine, or milrinone 2. Infusion of any vasopressor/inotropes above (yes vs. no) (identified by unit of weight over time) 3. Phenylephrine/ephedrine bolus (yes vs. no) (identified by unit of weight only) 4. Vasodilator use (yes vs. no): labetalol, esmolol, nitroglycerin, nitroprusside 5. Infusion of any vasodilator above (yes vs. no) (identified by unit of weight over time)
Oxygen saturation by pulse oximetry: SpO₂	
 1. Longest single episode (minutes) below a) 88, and b) 90% 2. Cumulative duration (minutes) below a) 88, and b) 90%
End-tidal (i.e. exhaled) Carbon dioxide: EtCO₂	
 1. Longest single episode (minutes) a) below 30, and b) above 45mmHg 2. Cumulative duration (minutes) a) below 30, and b) above 45mmHg

II. Outcomes

Primary: 30-day all-cause postoperative mortality (binary)

Secondary:

1. Major 30-day in-hospital morbidity, both in terms of the individual category (yes/no), and an overall composite (i.e. yes for any of the 6 categories vs. no). We have included major morbidity outcomes where increased monitoring would be beneficial, using International Statistical Classification of Diseases (ICD) 10 codes and based on published protocol on patient safety indicators (27).
 1. Cardiac: composite of acute myocardial infarction, cardiac arrest, ventricular tachycardia, congestive heart failure, pulmonary edema, complete heart block, shock excluding septic shock
 2. Respiratory: composite of pneumonia, pulmonary embolism, acute respiratory failure, respiratory arrest, Mechanical Ventilation \geq 96 hours
 3. Acute Kidney Injury
 4. Cerebrovascular: composite of strokes and transient ischemic attacks

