			
Comorbidity covariates: We need the following DXCODE (with “DXTYPE[1-n] = 1”, OR “DXTPRE[1-n] = 2 AND DXPRE[1-n] = 5”, OR “DXTYPE[1-n] = 3 AND DXPRE[1-n] = 5”, OR “DXTYPE[1-n] = M AND DXPRE[1-n] = 5”) within 3 years before PDATE: Disease categories for RCRI (please see “RCRI”); hypertension (I10-I15), COPD (I27.8, I27.9, J40.x–J47.x, J60.x–J67.x, J68.4, J70.1, J70.3), Obesity (E66)
 
Postoperative outcomes: We need the following DXCODE (with “DXTYPE [1-n]=2” Excluding “DXTYPE [1-n]=2 AND DXPRE [1-n]=5”, OR “DXTYPE [1-n]=3” excluding “DXTYPE [1-n]=3 AND DXPRE [1-n]=5”, OR “DXTYPE[1-n] = M AND DXPRE[1-n] = 6”) to include into model as individual, categorical, and composite secondary outcome:
 
Cardiac: acute myocardial infarction (I21 to I22, I24), cardiac arrest (I46.0, 146.1, I46.9), ventricular tachycardia (I47.2), shock (R57, T81.1) excluding septic shock (R57.2), congestive heart failure (I50.0, I50.1, I50.9), pulmonary edema (J81), complete heart block (I44.2)
 
Respiratory: pneumonia (J13 to J18, J69.0, J69.8, J95.4), pulmonary embolism (I26), acute respiratory failure (J95.1, J95.2, J96.0), respiratory arrest (R9.2)

--	--	--	--

				
Cerebrovascular: strokes and transient ischemic attacks (I60 to I69, G45)
 
Delirium (F5)
 
Acute kidney injury (N17)
 
Septic shock (R57.2)

CIHI DAD	DXPRE [1-n]: diagnosis prefix	Patient	Jan 1, 2010 to Dec 31, 2017 (3 years before and including 30 days after date of surgery)	
To categorize the type of the corresponding DXCODE (please see above):
 
C = Cause of death Q = Query Diagnosis/Etiology 5 = Comorbidity arose before qualifying intervention 6 = Comorbidity arose during or after qualifying intervention 8 = Palliative Care

CIHI DAD	DXTYPE [1-n]: diagnosis type	Patient	Jan 1, 2010 to Dec 31, 2017 (3 years before and including 30 days after date of surgery)	
To categorize the type of the corresponding DXCODE (please see above):
 
M = Most Responsible Diagnosis 1 = Pre-admit comorbidity 2 = Post-admit comorbidity 3 = Secondary Diagnosis

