CIHI-DAD	Admit-date	Patient	1Jan2010 to 31Dec2017	
For 3-year look-back window with: either admission date or discharge date is between surgery date (B) and 3 years before B (A), assuming that A<B.
 
For 30-day follow-up window with: Either admission date or discharge date is between surgery date (B) and 30 days after B (C), assuming that B<C.

CIHI-DAD	Discharge_date	Patient	1Jan2010 to 31Dec2017	For 3-year look-back window with: either admission date or discharge date is between surgery date (B) and 3 years before B (A), assuming that A<B.

				For 30-day follow-up window with: Either admission date or discharge date is between surgery date (B) and 30 days after B (C), assuming that B<C.
CIHI DAD	ECI: Elixhauser comorbidity index [Derived by HDNS]	Patient	Jan 1, 2010 to Dec 1, 2017 (3 years before and including date of surgery)	
To be computed by the HDNS according to protocol (32) using DXCODES (please see above), to be included into model as covariate. Please report both total score, and any of the following individual categories:
 
Congestive heart failure Cardiac arrhythmias Valvular disease Pulmonary circulation disorders Peripheral vascular disorders Hypertension, uncomplicated Hypertension, complicated Paralysis Other neurological disorders Chronic pulmonary disease Diabetes, uncomplicated Diabetes, complicated Hypothyroidism Renal failure Liver disease Peptic Ulcer Disease Excluding Bleeding AIDS/HIV Lymphoma Metastatic cancer Solid tumor without metastasis Rheumatoid arthritis/ collagen vascular diseases Coagulopathy Obesity Weight loss Fluid and electrolyte disorders Blood loss anemia Deficiency anemia Alcohol abuse Drug abuse Psychoses

				Depression

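### The 30-day morbidity filter rejects type 1 codes, and type M codes without prefix 6, on readmission records that the follow-up window brings in

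*Combined protocol and SAP*

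**What the plan says.** - **Outcome.** Outcomes, Secondary 1: "Major 30-day in-hospital morbidity, both in terms of the individual category (yes/no), and an overall composite". The composite there is positive when any of six categories is positive. The section does not say whether a later admission counts as in-hospital.
- **Filter.** Appendix 1, DXCODE row, postoperative outcomes: a listed code counts if it is type 2 without prefix 5, type 3 without prefix 5, or "DXTYPE[1-n] = M AND DXPRE[1-n] = 6". The row says the codes are "to include into model as individual, categorical, and composite secondary outcome".
- **Meaning of the fields.** DXTYPE row: "M = Most Responsible Diagnosis 1 = Pre-admit comorbidity 2 = Post-admit comorbidity 3 = Secondary Diagnosis". DXPRE row: "6 = Comorbidity arose during or after qualifying intervention". The DXPRE row does not say whether the intervention must lie on the same hospital record.
- **Records in the window.** Admit-date and Discharge_date rows, 30-day follow-up: "Either admission date or discharge date is between surgery date (B) and 30 days after B (C), assuming that B<C".
- **Scope stated elsewhere.** The Date of surgery and PDATE rows say that linkage is meant to keep only the index surgical admission. The PDATE row then adds that variables other than comorbidity are needed for 30 days after the procedure.
- **Composite.** The Composite morbidity row counts two flags (heart resuscitation, ventilation of 96 hours or more) or any listed ICD code. It repeats no type or prefix condition.
- **Default.** Missing data: a patient without the ICD code is taken not to have the condition.

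**The concern.** A filter built on diagnosis type and prefix separates what was present before a stay from what arose in it. For the surgical stay this is what is wanted. On a readmission record the same logic can work backwards. A pneumonia that began at home on day 8 and caused the return is a new postoperative event relative to the surgery, but it preceded that admission, so "1 = Pre-admit comorbidity" describes it.

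Morbidity is the subject of the secondary hypothesis, and the best-performing model is to be used to find predictors of the secondary outcomes. If the same complication counts when the patient is still in hospital but not when it brings the patient back, ascertainment depends on when the patient was discharged. Length of stay plausibly tracks type and duration of surgery, so the error need not be unrelated to the hemodynamic exposures. The documents do not allow that distortion to be quantified.

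**Working it through.** The plan states no morbidity or readmission rate, so there is no figure of its own to reproduce.

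**Step 1. The filter as a rule.** Accept if (type 2 and prefix not 5), or (type 3 and prefix not 5), or (type M and prefix 6). Over all types and prefixes in Appendix 1:

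| Type | blank | 5 | 6 | C, Q or 8 |
|---|---|---|---|---|
| M | reject | reject | accept | reject |
| 1 | reject | reject | reject | reject |
| 2 | accept | reject | accept | accept |
| 3 | accept | reject | accept | accept |

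Type 1 never passes. Type M passes only with prefix 6.

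**Step 2. Which records are searched.** An admission starting on day 10 has its admission date within 30 days after surgery, so it meets the window rule. The DXCODE row's time span also runs to 30 days after surgery, and no separate rule is given for a later record.

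**Step 3. One patient, two discharge dates.** Pneumonia arises on day 8.
- Still in hospital: coded type 2 on the index record and accepted.
- Discharged on day 4, readmitted on day 10: if coded type 1, rejected. If coded M, rejected unless prefix 6 is present. With no other accepted code, the patient scores no respiratory morbidity.
- A further complication arising during that readmission and coded type 2 is accepted.

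Applied as written, the two rules count secondary events on a readmission but can drop the reason for it. That matches neither an index-stay outcome nor a full 30-day outcome.

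**Step 4. Composite against components.** Under the Composite morbidity row taken alone, the readmitted pneumonia scores yes, because any listed code suffices. Under the DXCODE row, the respiratory category scores no. The composite can then be positive with all six categories negative, against its definition in Outcomes. Read literally, the composite row would also admit prefix 5 codes, which the DXCODE row excludes.

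**Step 5. Possible size.** N = 35,000 is the plan's figure; the rates are assumptions.

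Patients affected = N × readmitted within 30 days × share returning with a listed diagnosis.
- Low: 35,000 × 0.04 × 0.10 = 140
- Middle: 35,000 × 0.07 × 0.20 = 490
- High: 35,000 × 0.10 × 0.30 = 1,050

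These assume that every such event is rejected. If half pass (as type 3, or M with prefix 6), the range is 70 to 525.

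For a composite governed by the DXCODE filter, assume index-stay morbidity of 5–15% (1,750 to 5,250 patients) and no overlap with the affected patients. Sensitivity = detected / true:
- Best case, all rejected: 5,250 / (5,250 + 140) = 0.97
- Worst case, all rejected: 1,750 / (1,750 + 1,050) = 0.63
- Worst case, half passing: (1,750 + 525) / 2,800 = 0.81

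**The case against.** **Index stay only.** The Date of surgery and PDATE rows, and Step 2 of Data linkage, speak of data from the same surgical admission. The outcome is called in-hospital, and readmission is a separate secondary outcome. The follow-up window sits in the date-field rows, does not mention morbidity, and could serve readmission and days alive and out of hospital. On that reading the filter fits its purpose. This stands as a possible reading, but it does not remove the problem: nothing confines the morbidity search to the index record, and the outcome carries a 30-day label.

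**The stronger reading.** A reader might infer that the filter cannot recognise any complication that brings a patient back, so that all such patients score as free of morbidity. The documents do not support that:
- Types 2 and 3 without prefix 5, and M with prefix 6, all pass.
- That prefix 6 refers only to an intervention on the same record is not stated. If it refers to the index surgery, a readmission infarction coded M with prefix 6 is accepted. The exclusion of type 1 does not depend on this.
- The two flags carry no type or prefix condition, and the composite row repeats none for ICD codes.
- A patient with an accepted code from the index stay is already positive on the composite.

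**Limited consequence.** The primary outcome comes from Vital Statistics, and the Limitations section already concedes misclassification and ascertainment bias. Both points are right and keep this a secondary-outcome matter. A general caveat does not settle a derivation rule that can still be corrected.

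**Conclusion.** The concern holds in limited form. With the DXCODE filter and the 30-day window applied as written, readmission complications coded type 1, or M without prefix 6, are scored as absent, while type 2 and 3 codes on the same records count. The individual and category morbidity outcomes are under-ascertained for patients whose complication appears after discharge. The composite has two derivations that can disagree, and the Appendix rows point to two different scopes.

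The size is unknown. The range of 140–1,050 out of 35,000 is an upper bound under assumed readmission and diagnosis rates, because it treats every such event as lost. Thirty-day mortality is unaffected. The point should be resolved before the outcome variables are derived, but it does not threaten the primary analysis.

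**What to change.** Make the Date of surgery, PDATE, DXCODE, Admit-date/Discharge_date and Composite morbidity rows agree on one scope.

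**(a) If readmissions count towards 30-day morbidity.** Keep the current filter for the index admission. For admissions starting after index discharge and within 30 days of PDATE, also accept:
- listed acute codes of type M, other than query diagnoses;
- type 1 only for codes that cannot represent chronic or prior disease (so not, for example, heart failure or late-effect codes within I60–I69).

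Confirm with HDNS which intervention prefixes 5 and 6 refer to, since that decides how they should act on a readmission record. Apply the same rule in the Composite morbidity row.

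**(b) If only the index stay is intended.** Search only the index record for morbidity codes, rename the outcome *index-admission morbidity within 30 days*, and put the same condition in the Composite morbidity row. Keep the 30-day window for readmission and for days alive and out of hospital.

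Either option costs a few lines in the HDNS derivation, on fields already requested. The downside of (a) is that a few type 1 codes on readmission may be pre-existing disease, which the restriction on type 1 is meant to limit.

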Since intraoperative hemodynamics are automatically recorded and mortality reporting is mandatory, we do not expect significant missing data for the key hemodynamic predictors and primary outcomes. For disease conditions, patients without ICD codes are assumed to not have the disease; the same applies for medications. For the other variables of interest, if there is less than 5% missing data, no processing will be performed. Between 5-20%, missing data will be imputed using group mean (43) for continuous variables. At greater than 20% missing data, the variable will be removed from analysis with potential causes evaluated and reported.

Creating the models

We will divide the cohort temporally (approximately 80:20 ratio) into two groups: derivation/training group (approx. January 1, 2013 – Dec 31, 2016), and validation group (approx. Jan 1, 2017 – December 1, 2017). This temporal approach to the model building vs. validation groups will also mirror the real-life application of machine learning, where data from the past is used to predict future outcomes. Splines will be used for the hemodynamic predictors involving time as a unit.

In the derivation/training set, we will create models for the *primary outcome* using machine learning techniques, including logistic regression with variable selection, classification trees, and Principal Component Analysis (PCA)(21). We have chosen these techniques to obtain interpretable results, i.e. being able to understand the process by which the algorithm decision making occurred. Also, these techniques demonstrate different approaches and perspectives to better understand the relationships amongst the variables.

Logistic regression with variable selection (e.g. LASSO, Elastic Net) identifies the most important predictors to create a parsimonious model. Classification trees predict outcomes based on input variables through classification. Random forest is an ensemble method of classification trees; while it is not directly interpretable, it can show which predictor has the highest importance. Association rule learning will be used to find new patterns. PCA is used for

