			
J96.0), respiratory arrest (R9.2), strokes and transient ischemic attacks (I60 to I69, G45), Delirium (F05), Acute kidney injury (N17), Septic shock (R57.2)
 
Causes not fitting the above secondary outcomes will be categorized according to standard ICD categories:
 
Infectious diseases (A00-B99)
 
Neoplasm (C00-D48)
 
Diseases of the blood and blood-forming organs and certain disorders involving the immune mechanism (D50-D89)
 
Endocrine, nutritional and metabolic diseases (E00-E90)
 
Mental and behavioural disorders (F00-F99)
 
Diseases of the nervous system (G00-G99)
 
Diseases of the circulatory system (I00-I99)
 
Diseases of the respiratory system (J00-J99)
 
Diseases of the digestive system (K00-K93)
 
Diseases of the skin and subcutaneous tissue (L00-L99)
 
Diseases of the musculoskeletal system and connective tissue (M00-M99)
 
Diseases of the genitourinary system (N00-N99)
 
Pregnancy, childbirth and the puerperium (O00-O99)
 
Congenital malformations, deformations and chromosomal abnormalities (Q00-Q99)

--	--	--	---

				
Injury, poisoning and certain other consequences of external causes (S00-T98)
 
External causes of morbidity and mortality (V01-Y98)
 
Causes not fitting any of the above categories will be coded as UCAUSE = other
 
Descriptive statistics will be performed for causes.

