CIHI DAD	FLAG_HE_ARTRESUS : Heart Resuscitation Flag	Patient	Jan 1, 2013 to Dec 31, 2017	Part of secondary outcomes to be included into model. Descriptive statistics will be performed for this subcategory, within the category of cardiac complications, and an overall composite measure of each category. 0 = No 1 = Yes
CIHI DAD	FLAG_ME_CHVEN_G_E96: Mechanical Ventilation \geq 96 hours	Patient	Jan 1, 2013 to Dec 31, 2017	Part of secondary outcomes to be included into model. Descriptive statistics will be performed for this subcategory, within the category of respiratory complications, and an overall composite measure of each category. 0 = No 1 = Yes
CIHI DAD	Composite morbidity [Derived by HDNS]	Patient	Jan 1, 2013 to Dec 31, 2017	Binary variable (yes/no) derived based on any of the following: FLAG_HEARTRESUS, FLAG_MECHVEN_GE96, or ICD code of any of: acute myocardial infarction (I21 to I22, I24), cardiac arrest (I46.0, I46.1, I46.9), ventricular tachycardia (I47.2), shock (R57, T81.1) excluding septic shock (R57.2), congestive heart failure (I50.0, I50.1, I50.9), pulmonary edema (J81), complete heart block (I44.2), pneumonia (J13 to J18, J69.0, J69.8, J95.4), pulmonary embolism (I26), acute respiratory failure (J95.1, J95.2, J96.0), respiratory arrest (R9.2), strokes and transient ischemic attacks (I60 to I69),

				
G45), Delirium (F05), Acute kidney injury (N17), Septic shock (R57.2)
 
Part of secondary outcomes to be included into model. Descriptive statistics will be performed.

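### Respiratory arrest is coded R9.2 in all four Appendix 1 lists, a code one digit short that would not capture the condition if applied as written

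*Combined protocol and SAP*

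**What the plan says.** The Outcomes section makes respiratory arrest part of major 30-day in-hospital morbidity: "Respiratory: composite of pneumonia, pulmonary embolism, acute respiratory failure, respiratory arrest", with mechanical ventilation of at least 96 hours as the fifth component. Respiratory is one of six categories that feed the overall composite.

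Appendix 1 turns these conditions into ICD codes. In the DXCODE row, under postoperative outcomes, the entry is "respiratory arrest (R9.2". The rows for underlying cause of death, all causes of death and composite morbidity each carry the same string: "respiratory arrest (R9.2), strokes and transient ischemic attacks".

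Neighbouring entries are fully formed, for example "acute respiratory failure (J95.1, J95.2, J96.0" and, with the same initial letter, "septic shock (R57.2".

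Two further statements decide what happens to an unmatched code:

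- The composite morbidity row has HDNS derive a yes/no variable from "FLAG_HEARTRESUS, FLAG_MECHVEN_GE96, or ICD code of any of" the listed conditions.
- The Missing data section says "patients without ICD codes are assumed to not have the disease".

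**The concern.** These lists are the operative outcome definitions that the data custodian is asked to apply. A code that does not identify its condition produces a recorded ‘no’, not a missing value, because absence of a code is read as absence of disease.

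Respiratory arrest enters in three places: as an individual variable, within the respiratory category and composite, and in the descriptive cause-of-death flags. The DXCODE row asks for outcomes at the individual, category and composite levels, so the individual variable is wrong even for patients whom another component brings into the composite.

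The cause-of-death rows add a further consequence. Causes not matched to a named condition go to broad ICD chapters, but those fallback lists pass from Q00-Q99 to S00-T98 with no R chapter. A death attributed to respiratory arrest under an R code would therefore end up in the residual ‘other’ group.

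**Working it through.** No sample-size or power figure is involved. The check is one of code format and string matching.

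**Step 1: the code in each list, beside two others that look irregular.**

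| Appendix 1 row | Respiratory arrest | Delirium | Second and third cardiac-arrest codes |
|---|---|---|---|
| DXCODE, postoperative outcomes | R9.2 | F5 | 146.1, I46.9 |
| Underlying cause of death | R9.2 | F05 | 146.1, 146.9 |
| All causes of death | R9.2 | F05 | 146.1, I46.9 |
| Composite morbidity | R9.2 | F05 | I46.1, I46.9 |

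Delirium and cardiac arrest each have a well-formed version in at least one list. Respiratory arrest has none.

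**Step 2: format.** 71 code strings from Appendix 1 (single codes and range endpoints) were tested against the documents' own pattern: one letter, two digits, optional decimal digit. 68 fit and three do not: R9.2, F5 and 146.1. The 146.9 in the underlying-cause row was not among the 71; it is irregular in the same way as 146.1.

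**Step 3: what the short codes would match.** The comparison set is every string from A00 to Z99, alone or with .0 to .9: 26 × 100 × 11 = 28,600 strings.

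| Matching rule | R9.2 | F5 |
|---|---|---|
| Exact | 0 | 0 |
| Prefix | 0 | 10 × 11 = 110 (F50 to F59.9), none of them F05 |
| Prefix, dots removed | 11 (R92 and R92.0 to R92.9) | the same F50 to F59.9 strings |

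R92 is not listed for any outcome. Under no rule does R9.2 match a code beginning R09, which is where a dropped leading zero would place it. The documents do not state that code, so it is only a conjecture suggested by the F5/F05 pair.

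**Step 4: who is misclassified.** With respiratory arrest uncaptured, a patient who had it is scored:

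- ‘no’ for the respiratory category if none of the other four components is recorded;
- ‘no’ for the composite if, in addition, neither derivation flag (heart resuscitation, ventilation of 96 hours or more) and no other listed code is present.

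**Step 5: could this be a text-extraction fault?** It is unlikely for R9.2: the string is identical in four places, and F05 keeps its zero in three of the same lists. For 146.x it is quite possible, since 1 and I are easily confused and the composite row prints I46.1.

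**The case against.** The strongest reply is that this is a typographical slip that a competent custodian would catch. Each list prints the condition's name beside the code, the Outcomes section says the morbidity codes follow a published protocol on patient safety indicators, and the dataset is to be built by experienced HDNS staff. The plan also promises descriptive statistics on every outcome, so an empty variable might be noticed. All of that is fair, and it means silent failure is not certain. It does not remove the point: the written definition is still wrong, any repair would be an unrecorded judgement, and nothing in the plan asks for a count per code or a query on zero matches.

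A reader might infer that the component is bound to be zero for everyone and that every respiratory arrest is lost. The documents do not support that. They state no matching rule; with dots removed the string would pick up an unrelated block, which adds false events to the missed ones. A patient with respiratory arrest may also still be counted through another component.

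A reader might also treat 146.1 as a second established coding error. It is more safely treated as something to confirm in the source file.

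Finally, it is fair to say that the effect is confined to one of five components of one of six categories in a secondary composite, plus descriptive cause-of-death tables. That limit stands.

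**Conclusion.** The point holds as a defect in the outcome definitions. R9.2 is malformed in all four lists, has no correct counterpart in the documents, and under each of the three matching rules tried would fail to capture respiratory arrest. Combined with the rule that no code means no disease, patients whose only listed complication is respiratory arrest would be counted as event-free in the respiratory category and the composite.

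The size cannot be stated: the documents give no frequency for respiratory arrest, alone or with other complications. The conclusion assumes that the code is applied as printed; if HDNS corrects it unprompted, the loss disappears but the written definition remains wrong. The primary outcome is untouched, because it is derived from date of death.

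The delirium entry F5 in the DXCODE row is a slip of the same kind and concerns a whole outcome category. Taken literally, it would also set that row at odds with the composite row: an F05 record would count in the composite but not in the delirium category.

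**What to change.** Before HDNS derives any outcome:

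1. Verify the respiratory-arrest code against the ICD-10 table that HDNS uses, and correct it in the DXCODE, underlying cause of death, all causes of death and composite morbidity rows.
2. Change the delirium code F5 in the DXCODE row to agree with F05 in the other three rows.
3. Confirm in the source file that the 146.x strings in the DXCODE, underlying cause of death and all causes of death rows read I46.x, as in the composite morbidity row.
4. Ask HDNS to return a count per listed code and to query any code with zero matches before the category and composite variables are built. A zero count will not expose a short code that matches the wrong block, so steps 1 and 2 are needed as well.

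The cost is a few edits to one appendix and one frequency table from HDNS. The analysis methods and the sample are unchanged.
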